### 17.1.2 Deaths and Serious Adverse Events

A listing of deaths and other SAEs will be provided for all subjects.

### 17.1.3 Laboratory Data

Clinical laboratory data will be presented using units from the study data tabulation model (SDTM) Controlled Terminology.

A descriptive statistics summary of continuous laboratory results for clinical chemistry, hematology and derived changes from baseline will be provided by treatment and scheduled time point.

Shift tables describing the change in clinical laboratory values from baseline to each post-dose scheduled time point (number and percentage of subjects) will also be provided by treatment. The following categories will be used: low, normal, and high.

All laboratory data will be listed by subject, including laboratory variables not listed in the protocol.

A separate listing of out-of-range values will also be provided. Normal ranges will be used directly from the clinical laboratory and will be included in the listings for reference.

#### 17.1.4 Vital Signs

A descriptive statistics summary of vital signs and derived changes from baseline will be provided by treatment and scheduled time point.

If considered informative by the data obtained, plots of the mean change from baseline for the vital signs parameters versus time since dosing will be presented by part and treatment.

All vital signs data will be listed by subject.

#### 17.1.5 Electrocardiograms

The observed measurements for all ECG parameters and the corresponding abnormalities will be listed for all time points. The means of triplicate measurements for continuous parameters and the change from baseline of the mean triplicate measurements at each scheduled time point will be listed by subject.

Descriptive statistics will be provided to summarize mean ECG parameters (observed and changes from baseline) by treatment and scheduled time.

QTC prolongation potential will be by scatter Plot of change from baseline of QTcF versus BMS-986251 plasma concentration.

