Within each cohort, safety, PK, and PD assessments will be performed. The bioanalytical personnel responsible for performing the analyses of the PK samples will be unblinded throughout the study to prevent unnecessary analysis of placebo samples. Following completion of each dose panel, there will be a review period between panels, during which all available safety, tolerability, PK, and PD data (as applicable) will be reviewed by the Sponsor's dose escalation review group. Limited designated staff of BMS and/or PRA can be unblinded at this time to prepare preliminary summaries of PK, PD and safety data. These summaries will not reveal individual subjects' treatment assignments and will include summaries and figures of mean data (as applicable). The Sponsor's dose escalation review group will review the data and will determine whether escalation to the next dose level will occur, or whether dose-stopping criteria have been met. The pharmacist at the site and/or designate will be unblinded to the randomized treatment assignments in order to dispense treatment from bulk supplies, as needed. Except as noted above, other members of BMS Research and Development and PRA will remain blinded.

Randomization schedules will be shipped directly to a pharmacist or other individual(s) who will be responsible for the dispensing of blinded study drug. This (these) individual(s) will be unblinded to study drug identification but will not be involved in any other aspect of study conduct. The randomization schedules will be maintained in a secure location with access limited to authorized personnel.

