8.5.2.7 Continuous Cardiac Monitoring (Holter Monitoring)

Continuous ECG monitoring will be performed to help monitor patient safety; primarily to detect ventricular and atrial arrhythmias. The site will follow their normal operating procedures established for ECG monitoring. Clinically significant findings from the monitoring will be recorded as AEs and SAEs per the Investigator's decision, and at the Investigator's discretion the study drug may be discontinued for clinically significant arrhythmias.

The ECGs collected by continuous monitoring will be stored for potential later use. These ECGs may or may not be analyzed for the purpose of Concentration Effect Modelling, based on future development decisions for BMS-986251. If analyzed, results of the modeling will not be included in the clinical study report, but will be included in a separate report.

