#### 8.1.4 Pooling

Summary statistics will be calculated by study part, treatment (and time point, if applicable). Placebo data will be pooled across cohorts in Part A for descriptive statistics.

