## 8.4.2 Predetermined Covariates and Prognostic Factors

There are no predetermined covariates or prognostic factors.

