### 9.3 Pharmacokinetic

The PK analysis set will consist of all subjects who receive at least 1 dose of BMS-986251 and have sufficient concentration-time data to calculate a valid Cmax and AUC(0-T).

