Table 14.4.4.2	Summary of Safety Laboratory Results	Safety
Table 14.4.4.3	Shift Summary of Laboratory Results by Reference Range and Time Point	Safety
Table 14.4.4.4	Summary of Vital Signs	Safety
Figure 14.4.4.5	Plots of mean change from baseline of Vital Signs	Safety
Table 14.4.4.6	Summary of 12-Lead Electrocardiograms	Safety

List of End of Text Listings:	
Output	Title
Section 16.2.1 – Disposition	
Listing 16.2.1.1	Subject Disposition
Listing 16.2.1.2	Tuberculosis Screening
Section 16.2.2 – Protocol Deviations	
Listing 16.2.2	Important Protocol Deviations
Section 16.2.3 – Excluded Subjects	
Listing 16.2.3	Analysis Sets
Section 16.2.4 – Demographics and Baseline Characteristics	
Listing 16.2.4.1	Subject Demographics
Listing 16.2.4.2	Medical History
Listing 16.2.4.3	Prior and Concomitant Medications
Listing 16.2.4.4	Tobacco and Alcohol Use
Section 16.2.5 - Compliance	
Listing 16.2.5.1	Study Drug Administration
Section 16.2.6 – Response Data	
Listing 16.2.6.1	Plasma BMS-986251 Concentrations
Listing 16.2.6.2	Plasma Pharmacokinetic Parameters
Listing 16.2.6.3	Urine BMS-986251 Concentrations and Amounts Excreted

Listing 16.2.6.4	Urine Pharmacokinetic Parameters
Listing 16.2.6.5	IL-17 Concentrations in Stimulated and Unstimulated Whole Blood
Listing 16.2.6.6	IL-17 Inhibition in Whole Blood
Listing 16.2.6.7	IL-17 Inhibition in Whole Blood Pharmacokinetic Parameters
Section 16.2.7 – Adverse Events Data	
Listing 16.2.7.1	Adverse Events
Listing 16.2.7.2	Adverse Events Leading to Study Drug Discontinuation
Section 16.2.8 – Laboratory Data	
Listing 16.2.8.1	Clinical Laboratory Results – Chemistry
Listing 16.2.8.2	Clinical Laboratory Results – Hematology
Listing 16.2.8.3	Clinical Laboratory Results – Urinalysis
Listing 16.2.8.4	Clinical Laboratory Results – Serology
Listing 16.2.8.5	Clinical Laboratory Results – Pregnancy
Listing 16.2.8.6	Clinical Laboratory Results – Drug and Alcohol Screen
Listing 16.2.8.7	Clinical Laboratory Results – Comments
Section 16.2.9– Other Safety Data	
Listing 16.2.9.1	Vital Signs
Listing 16.2.9.2	12-Lead Electrocardiograms
Figure 16.2.9.3	Scatter Plots of $\Delta$ QTcF Versus BMS-986251 Plasma Concentration
Listing 16.2.9.4	Physical Examinations
Listing 16.2.9.5	Taste Questionnaire

Other Appendix Outputs:	
Output	Title
Appendix 16.1.7	Randomization
Appendix 16.1.9.2	Statistical Appendices

---

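### SAP 17.1.5 assesses QTc prolongation potential by a scatter plot alone, with no time term, model or placebo reference, so a QTcF shift shared by all subjects early after dosing can mimic or mask a concentration effect

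*SAP*

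**What the plan says.** SAP 17.1.5 gives one tool for this question: "QTC prolongation potential will be by scatter Plot of change from baseline of QTcF versus BMS-986251 plasma concentration". SAP Appendix 4 lists the output as Figure 16.2.9.3, a set of scatter plots of change in "QTcF Versus BMS-986251 Plasma Concentration". It sits in the end-of-text listings, which have no analysis-set column. The table, figure and listing shells are a separate document.

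On placebo, Protocol 8.4.3.2 keeps the bioanalysts "unblinded throughout the study to prevent unnecessary analysis of placebo samples", and SAP 9.3 says: "The PK analysis set will consist of all subjects who receive at least 1 dose of BMS-986251". Nothing states that placebo subjects are entered in the QTcF plot at zero concentration. On covariates, SAP 8.4.2 says: "There are no predetermined covariates or prognostic factors". SAP 8.2.1 uses a single pre-dose baseline.

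The same ECG section also plans a table: "Descriptive statistics will be provided to summarize mean ECG parameters (observed and changes from baseline) by treatment and scheduled time". SAP 8.1.4 adds: "Placebo data will be pooled across cohorts in Part A for descriptive statistics". The output is Table 14.4.4.6.

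For the Holter recordings, Protocol 8.5.2.7 says: "These ECGs may or may not be analyzed for the purpose of Concentration Effect Modelling". Any such modelling goes to a separate report.

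**The concern.** A plot of change from baseline against concentration isolates a drug effect only if nothing else that moves QTcF travels with concentration. In Part A something may. Protocol 8.4.1.1 puts dosing at about 09:00 and keeps subjects fasted until at least 4 h afterwards. The 1, 2 and 8 h ECGs therefore fall at about 10:00, 11:00 and 17:00, and the 8 h ECG follows the first meal. The ECGs from 24 h on return to roughly the baseline clock time. The early window also contains the peak concentrations. A time-of-day, meal or procedure effect common to active and placebo subjects would load on the high-concentration end of the plot.

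At stake is the one statement the report will make about QTc prolongation potential. Randomised placebo subjects have ECGs at the same nominal times, so the information needed to separate time from drug is collected, but the stated assessment does not use it.

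**Working it through.** **The plan's own figure.** The documents give no QTc margin, SD or power. The only design probability concerns adverse events (SAP 6.1): 1 − 0.76^6 = 0.807, which agrees with the stated 80% or so and does not bear on QTc.

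**Inputs from the documents**
- Half-life about 40 h (Protocol 8.1.1), so k = ln 2 / 40 = 0.0173 per h.
- Doses 2, 6, 15, 30 and 60 mg; 8 subjects dosed in each of A1 to A4 and 4 in A5 (SAP 7.1). At 6 + 2 per full cohort, A1 to A4 give 24 active and 8 placebo.
- Post-dose ECGs read from the Part A schedule as 1, 2, 8, 24, 48, 96, 144 and 240 h, eight times. The table layout is imperfect in the extracted text.

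**Assumed inputs**
- Absorption rate ka of 0.5, 1 or 2 per h, one compartment.
- A5 split of 2, 3 or 4 active out of 4 (the SAP gives only n = 4), hence 10, 9 or 8 placebo in all.
- A shift of +5 ms in every subject, active or placebo, at 1, 2 and 8 h, and none later. No drug effect.

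**Formulas.** C(t) = D · ka/(ka − k) · (e^(−kt) − e^(−ka·t)), in arbitrary units. Three least-squares fits, each read at the highest 60 mg concentration among the ECG times:
1. Active subjects only: change = a + b·C.
2. The same line with placebo added at C = 0.
3. Placebo at C = 0, a level for each nominal time, and an active/placebo term.

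**Results.** For ka = 1 and a 3/1 split, fit 1 gives intercept 1.18 plus slope part 4.22 = 5.40 ms. Over all nine combinations of ka and split:

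| Fit | Apparent effect at 60 mg peak (true value 0) |
|---|---|
| 1. Active only | 4.7 to 6.2 ms |
| 2. Placebo at zero, no time term | 4.5 to 5.8 ms |
| 3. Placebo at zero, time and treatment terms | 0 ms |

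**Masking.** With a true effect of 10 ms at the 60 mg, 8 h concentration and a shared −5 ms shift over 1 to 8 h (3/1 split), fit 1 reads 4.6 to 5.0 ms. Fit 3 returns 10 ms.

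**Other windows (3/1 split, read at the 8 h concentration).** A +5 ms shift lasting 1 to 2 h, 1 to 8 h or 1 to 24 h gives 2.1 to 6.9 ms overall in fit 1. A +5 ms shift at every post-dose time gives slope zero and a level error of 5 ms.

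**Precision of fit 3.** With assumed within-subject SD 6 ms, between-subject SD 5 ms and 30% spread in exposure, the simulated SD of the 60 mg estimate is 3.6, 4.05 and 4.4 ms for 4, 3 and 2 active subjects at 60 mg. For three, a 90% interval is about ±1.645 × 4.05 = ±6.7 ms.

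**The case against.** The strongest reply is Table 14.4.4.6. It reports ECG change from baseline by treatment and scheduled time with Part A placebo pooled, so a shift common to everyone would appear in the placebo rows. That stands: the plot misleads only a reader who takes it alone. But the SAP does not tie the table to the plot, plans no placebo-corrected difference or interval, and names the plot, not the table, as the assessment of prolongation potential.

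Three stronger readings are tempting, and the documents do not support them.
- **The plot is stated to be active-only.** It is not. The reading is a good inference: placebo samples are not meant to be assayed, and SAP 16.2.1 names placebo explicitly for the individual IL-17 plots but 17.1.5 does not for this one. The separate shells could still show placebo at zero.
- **High concentrations occur only in the hours after dosing.** With a 40 h half-life, the 24 h concentration is still 69 to 77% of peak under the assumed ka, so 60 mg at 24 h exceeds the 30 mg peak at a matched clock time. The low-dose cohorts also supply early points near zero concentration. The overlap of time and concentration is partial.
- **The plot drives the primary ECG endpoint.** SAP 5.1.1 counts subjects with potentially clinically significant changes. The plot does not feed that count.

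It is also fair that the SAP fits no line to the plot, so the figures above describe what a least-squares reading of it would show. No formal testing is planned, and the study had already stopped for non-clinical reasons. The Holter deferral is not an answer, since it covers the continuous recordings and not the triplicate 12-lead ECGs.

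**Conclusion.** The point holds as an inexpensive improvement to an exploratory safety reading. The stated QTc assessment has no time term, model or placebo reference, and a shared early shift of 5 ms could read as an apparent effect of about 5 to 6 ms at the 60 mg peak, or hide about half of a true 10 ms effect. Adding placebo at zero concentration is not enough by itself; the time term does the work.

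The size depends on assumed shift size and duration, absorption rate and A5 split. The documents give no evidence that such a shift occurred. The direction of the bias follows from the ECG and dosing schedule. A shift that is constant over all post-dose times would leave the slope unbiased.

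**What to change.** In SAP 17.1.5:
- State that placebo subjects are plotted at concentration zero and marked as placebo, and give Figure 16.2.9.3 an analysis set.
- Add one exploratory linear mixed model for Part A: change in mean-triplicate QTcF on concentration, active/placebo indicator, nominal time (as a factor) and baseline QTcF, with a random subject effect.
- Report the placebo-corrected change at the geometric mean Cmax of each Part A dose with a 90% confidence interval, to be read beside Table 14.4.4.6.
- Note the exception in SAP 8.4.2, which at present names no covariates. An interval labelled exploratory is compatible with SAP 8.4.3.

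The cost is a paragraph, one model and one table, using ECG, concentration and placebo data already collected. Precision is limited because only 4 subjects were dosed in A5, so the result should be presented as a description with its uncertainty and not as evidence that a QT effect is absent. If the model is not wanted, the minimum is to say whether placebo is plotted, show placebo-corrected change by nominal time beside the figure, and stop describing the plot alone as the assessment of prolongation potential.

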## Appendix 1: Glossary of Abbreviations

Glossary of Abbreviations:	
AE	Adverse event
ADaM	Analysis data model
BA	Bioavailability
BMI	Body mass index
BMS	Bristol-Myers Squibb Research and Development
BLQ	Below the limit of quantification
CDISC	Clinical Data Interchange Standard Consortium
CSR	Clinical study report
CTMS	Clinical Trial Management System
CV	Coefficient of variation
DBP	Diastolic blood pressure
ECG	Electrocardiogram
eCRF	Electronic case report form
EDS	Early Development Services
FE	Food effect
FSH	Follicle stimulating hormone
HBsAg	Hepatitis B surface antigen
HCV	Hepatitis C virus
HIV	Human immunodeficiency virus
I	Inhibition
ICH	The International Conference on Harmonization of Technical Requirements for Registration of Pharmaceuticals for Human Use
IL	Interleukin
LLOQ	Lower limit of quantification
MAD	Multiple ascending dose
Max	Maximum
MedDRA	Medical Dictionary for Regulatory Activities
Min	Minimum
PD	Pharmacodynamic
PK	Pharmacokinetic
Pso	Psoriasis
QC('d)	Quality control(led)
QD	Once daily

SAD	Single ascending dose
SAP	Statistical analysis plan
SAE	Serious adverse event
SBP	Systolic blood pressure
SD	Standard deviation
SDTM	Study data tabulation model
SOC	System organ class
tbd	To be determined
TB	Tuberculosis
TBNK	T, B, and natural killer cells
TEAE	Treatment-emergent adverse event
TFL(s)	Tables, figures and listings
WHO	World Health Organization
WNL	WinNonlin

## Appendix 2: Schedule of Assessments from Protocol

**Table 7 Study Procedural Outline Part A – SAD Healthy Subjects (IM024 005)**

Visit	Screening	Pre-Treatment	Period 1 Period 2 (Cohort for Bioavailability and Food Effect Assessment only) Period 3 (Cohort for Bioavailability and Food Effect Assessment only)																		Follow-up 			
			Treatment																					
Study Days	-21 to -1	-1	1										2	3	4	5	6	7	9	11				
Time Post-Dosing (hrs)			Pre-dose	0	0.5	1	1.5	2	3	4	6	8	12	24	36	48	72	96	120	144	192	240		
Confinement			X																					
Discharge 																					X			
Ambulant visit	X																					X	X	
Informed consent and medical history	X																							
Demographics	X																							
Physical examination	X																						X	
Genotyping(CYPs, transporters) 				X																				
Vital signs	X		X			X		X		X		X		X		X	X	X	X	X	X	X	X	
Body weight and height (including BMI calculation) 	X	X																					X	
Eligibility check	X	X	X																					
12-lead ECG (triplicate)	X		X			X		X				X		X		X		X		X			X	

 For relative bioavailability/food effect cohort follow-up assessments on Day 11 of Period 3 only. At the Day 11 visit in Period 1 and 2 only blood sampling for PK and PD (Period 1 only), vital signs, and drug and alcohol screen will be performed.

 Discharge from the clinical research unit.

 Mandatory whole blood collection for analysis of DNA variants in ADME-related genes (<http://pharmaadme.org/Appendix 6>). For relative bioavailability/food effect cohort sample will be collected in Period 1 only. Sample may be taken at any time post-dose during Day 1.

 Height will only be measured at screening. BMI will also only be calculated at screening.

Visit	Screening	Pre-Treatment	Period 1																		Follow-up 		
			Period 2 (Cohort for Bioavailability and Food Effect Assessment only) Period 3 (Cohort for Bioavailability and Food Effect Assessment only)																				
Study Days	-21 to -1	-1	1 2 3 4 5 6 7 9																		11		
Time Post-Dosing (hrs)			Pre-dose	0	0.5	1	1.5	2	3	4	6	8	12	24	36	48	72	96	120	144	192	240	
Holter monitoring 			X 					X															
Clinical laboratory, hematology incl. reticulocytes	X	X												X		X				X			X
Drug and alcohol screen	X	X																				X	X
HBsAg, anti-HCV, and anti-HIV 1/2 tests	X																						
Quantiferon Gold test	X																						
FSH (females only)	X																						
Pregnancy test (females only)	X	X																					X
Overnight fast (10 hours)			X																				
Standardized lunch, snacks, dinner 								X															
High-fat breakfast 			X																				
Randomization			X																				
Study drug administration				X																			
Taste questionnaire				X 																			

 For bioavailability/food effect cohort in fasted Period 1 only

 Including a 15 minute supine period prior to every PK sample

 In triplicate in 3 supine periods

 In Period 1 with Holter monitoring only.

 In Period 3 of bioavailability/food effect cohort only

 To be completed immediately after drug administration (within first 10 seconds) and after approximately 1 minute (before drinking the provided glass of water)

Visit	Screening	Period 1																			Follow-up 	
		Pre-Treatment	Treatment																			
Study Days	-21 to -1	-1	1						2			3	4	5	6	7	9	11				
Time Post-Dosing (hrs)			Pre-dose	0	0.5	1	1.5	2	3	4	6	8	12	24	36	48	72	96	120	144	192	240
Previous and concomitant medications	X	X																				
PK sampling blood 		X	X	X	X	X	X	X	X	X	X	X	X	X	X	X	X	X	X	X	X	X
Urine collection for parent drug and metabolites		X	X						X	X	X	X	X	X	X	X	X	X	X	X	X	X
Sampling for ex-vivo IL-17 inhibition in whole blood 		X	X		X		X		X		X	X	X	X	X	X	X	X	X	X	X	X
Adverse events		X																				
Serious adverse events		X																				

BMI = body mass index; CYP = cytochrome P450; ECG = electrocardiogram; FSH = follicle stimulating hormone; HBsAg = hepatitis B surface antigen; HCV = hepatitis C virus; HIV = human immunodeficiency virus; hrs = hours; IL-17 = interleukin 17; PK = pharmacokinetic

 Including a 15 minute supine period prior to every PK sample during Holter monitoring

 Period 1 only

**Table 7 Study Procedural Outline Part B – MAD Healthy Subjects (IM024 005)**

Visit	Screening	Pre-Treatment	Treatment																	Follow-up		
Study Days	-21 to -1	-1	1 14 											2-13			15	16	18	20	24	
Time Post-Daily Dose (hrs) 			Pre-dose	0	0.5	1	1.5	2	3	4	6	8	12	Pre-dose	0	4	24	48	96	144	240	
Confinement			X																			
Discharge 																			X			
Ambulant visit	X																			X	X	X
Informed consent and medical history	X																					
Demographics	X																					
Physical examination	X																					X
Genotyping(CYPs, transporters) 				X																		
Vital signs	X		X			X		X		X		X		X		X	X	X	X	X	X	X
Body weight and height (including BMI calculation) 	X	X																				X
Eligibility check	X	X	X 																			
12-lead ECG (triplicate)	X		X			X		X				X				X 						X

 Schedule for Day 1 (first day of dosing) and Day 14 (last day of dosing).

 Time is given relative to dosing on the relevant study day. In the CRF, time “0” will be the time of first dosing and all other time points will be relative to time “0”.

 Discharge from the clinical research unit.

 Mandatory whole blood collection for analysis of DNA variants in ADME-related genes (<http://pharmaadme.org/Appendix 6>). Sample may be taken at any time post-dose during Day 1; no sample to be taken on Day 14.

 Height will only be measured at screening. BMI will also only be calculated at screening.

 Not on Day 14.

 Days 2, 4, 6, 8, 10, and 12 only.

Visit	Screening	Pre-Treatment	Treatment																		Follow-up	
Study Days	-21 to -1	-1	1 14 											2-13			15	16	18	20	24	
Time Post-Daily Dose (hrs) 			Pre-dose	0	0.5	1	1.5	2	3	4	6	8	12	Pre-dose	0	4	24	48	96	144	240	
Clinical laboratory, hematology incl. reticulocytes	X	X	X 											X 				X				X
Holter monitoring 			X 	X																		
Drug and alcohol screen	X	X																			X	X
HBsAg, anti-HCV, and anti-HIV 1/2 tests	X																					
Quantiferon Gold test	X																					
FSH (females only)	X																					
Pregnancy test (females only)	X	X																				X
Randomization			X 																			
Overnight fast (10 hours)		X																				
Standardized lunch, snacks, dinner				X																		
Study drug administration				X											X							
Taste questionnaire				X 																		
Previous and concomitant medications	X			X																		

 Day 14 only.

 Days 3, 7, and 10 only.

 Including a 15 minute supine period prior to every PK sample.

 If upcoming preclinical safety results indicate the need for a dedicated TQTc study, Holter monitoring for this study will be simplified and not plan for concentration-effect modeling.

 In triplicate in 3 supine periods.

 On Day 1 only.

 On Day 1 only. To be completed immediately after drug administration (within first 10 seconds) and after approximately 1 minute (before drinking the provided glass of water).

Visit	Screening	Pre-Treatment	Treatment																	Follow-up	
Study Days	-21 to -1	-1	1 14 											2-13			15	16	18	20	24
Time Post-Daily Dose (hrs) 			Pre-dose	0	0.5	1	1.5	2	3	4	6	8	12	Pre-dose	0	4	24	48	96	144	240
PK sampling blood 			X		X	X	X	X	X	X	X	X	X	X		X	X	X	X	X	X
Urine collection for parent drug and metabolites		X		X 																	
Sampling for ex-vivo IL-17 inhibition in whole blood		X	X			X		X		X			X	X 				X		X	X
Sampling for IL-17, IL-22, β-defensin, and erythropoietin			X														X				X
Sampling for T, B, and NK cells (TBNK), γδ T cells, T cell subsets.			X														X				X
Adverse events				X																	
Serious adverse events				X																	

 Including a 15 minute supine period prior to every PK sample during Holter monitoring.

 24-hours urine collection on Day 14 only

 Pre-dose at Days 2, 4 and 7 only.

